9.3 Definition of Populations

Because of the primary aim of feasibility, and corresponding dependent variables of recruitment and retention, we do not plan to differentiate ITT and per protocol populations for the analyses.

9.4 Interim Analyses and Stopping Rules

We have no plans for interim analyses.

9.5 Outcomes

Please see response to Section 9.1 above. We have no plans for outcomes to be reviewed and adjudicated by a committee.

9.5.1 Primary Outcome

The outcome for Aim 1 will be descriptive, including calculating the percent of individuals enrolled in the study versus those eligible and the percent of individuals who remain in the study. We will pay particular attention to issues of retention, as the treatment program will occur over 12 weeks and this length may impact treatment completion (previous programs of ACT alone, which have lasted eight weeks, have had drop-outs of < 20%^{17,21}. The assessment of this latter primary outcome will occur at each treatment meeting (as this is the only way to assess retention) and follow-up.

9.6 Data Entry and Analyses

Data will be entered into the Statistical Package for Social Sciences Software (SPSS; IBM Corp). We will update the software license yearly so that the most recent version is used (currently version 22 is used). We will use an audit trail for entry, which will include a "sign-in" mechanism, where each session of data entry will be recorded. Recorded information within this mechanism will include the RA doing data entry, as well as case numbers entered and descriptive information with regard to the data entered (e.g., "cases 14-19; post-treatment data entered". A new database will be saved and individually labeled after each session of data entry (e.g., NCCIH R34 – Jan.22.2015).

In addition to responses to section 9.1 and 9.2, where details regarding the data analyses can be found, the following information addresses the queries listed in the instructional set for completing this protocol. We do not anticipate any confounding variables, although we will assess for the role of gender, age, ethnicity, educational achievement, pain duration, and pain location in influencing dependent variables.

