9.1 General Design Issues

Preliminary Analyses: Data will be analyzed for missing cases to detect any bias across research groups that might result from differential attrition and/or response omission. For example, participant characteristics to include gender, minority status, age, drinking history, pain duration and intensity, educational achievement, and previous treatment experiences will be compared for those participants retained in the study versus those lost to attrition. Furthermore, the data will be examined for both missing cases and outlier scores on measures. Variable distributions will be checked for normality and if necessary, transformations will be performed to normalize the distributions. We will compare demographics and primary study measures at baseline between randomized treatment groups, using Analyses of Variance (ANOVA) for continuous variables (or Kruskal-Wallis if parametric assumptions are violated) and using chi-square tests for categorical variables. Subsequent analyses will adjust for significant baseline differences among the randomized groups at $\alpha = 0.05$.

Analyses to Test Primary Aim Hypotheses: The primary analyses for Aim 1 will be descriptive, including calculating the percent of individuals enrolled in the study versus those eligible and the percent of individuals who remain in the study. We will pay particular attention to issues of retention, as the treatment program will occur over 12 weeks and this length may impact treatment completion (previous programs of ACT alone, which have lasted eight weeks, have had drop-outs of < 20%^{17,21}). Therefore, we will define multiple levels of treatment retention, including partial treatment completion (% of individuals who do not complete all sessions), treatment dropout (% of individuals who dropout of treatment but continue to do assessments), research dropouts (% of individuals who remain in treatment, but do not complete research assessments), and treatment + research dropouts (% of individuals who do not complete treatment for research assessments). We will further break down the enrollment and retention calculations by examining enrollment/retention differences by treatment group, gender, age race/ethnicity, and initial severity using cross-classification tables.

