Analyses to Test Secondary Aim Hypotheses. The primary goal of Aim 2 is to identify potential mechanisms of change and intermediate endpoints for future randomized clinical trials comparing ACT+MBRP to standard care. We will accomplish this goal by examining initial level and changes in targeted mechanisms over time during the course of treatment, as well as the association between changes in targeted mechanisms during treatment and 6-month follow-up measures of clinical outcomes. Targeted mechanisms will include (1) pain acceptance (2) psychological flexibility, (3) experiential avoidance, (4) opioid craving, and (5) reactivity to pain and craving, and will be examined using latent growth curve models with fixed effects of treatment and random effects of time. These analyses will provide an estimate of the initial level of each targeted mechanism (i.e., intercept) and the change in the targeted mechanisms over time (slope). Clinical outcome measures will include pain interference, pain behavior, and opioid misuse and will be examined using mediation analyses within the context of latent growth curve modeling⁶⁴, as we have done in prior studies^{63,65}. Specifically, as shown in simplified form in Figure 2, we will examine whether initial level (intercept) or changes (slope) in the targeted mechanisms ("M" in figure 2) during treatment mediate the effect of treatment on 6-month clinical outcomes, controlling for baseline levels of the outcomes. These analyses will also provide a test of Aim 2 Hypothesis 2, which is to identify those measures that are most sensitive to change (measures with the largest slope). Identifying measures that are more sensitive to change will help us in identifying intermediate endpoints for a larger RCT. Validation of intermediate endpoints is challenging and it is often recommended that meta-analytic methods be used⁶⁶, but alternative methods have been developed that allow for the evaluation of endpoints in mental-health clinical trials⁶⁷.

Figure 2. Simplified mediation model (excludes residual terms and covariances)

models will be estimated using the product of coefficients method⁶⁸, which provides an estimate of the mediated effect by multiplying regression coefficients for the regression of the mediators (e.g., slope of targeted mechanism) on treatment condition (i.e., a-path or α) and for the regression of the clinical

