outcome on the mediators (i.e., b-path or β). We will use bootstrapping to obtain 95% confidence intervals of the mediated effect⁶⁹. We will use maximum likelihood estimation for all analyses, which provides the variance-covariance matrix for all available data and is the preferred method for estimation when some data are missing⁷⁰. Attrition analyses will determine whether there are any differences in study variables between those with missing and complete data. Study variables associated with missing data will be covaried in all analyses.

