9.2 Sample Size and Randomization

Commented [KV4]: Blocking

Statistical Power for Secondary Aims: We estimated statistical power for the mediation analyses using parameter estimates from prior studies of mediation following ACT for chronic pain⁵ and following MBRP for substance use disorders^{7,63} to estimate the effect sizes for the behavioral measures in the current study. Following ACT, numerous behavioral measures significantly mediated changes in disability, depression, pain-related anxiety, medical visits, and number of classes of prescribed analgesics, with large mediation effect sizes. The prior studies of MBRP have found that experiential avoidance, awareness, and nonjudgment significantly mediated the association between treatment and changes in craving ($\alpha = 0.56$; $\beta = -0.43$) and that craving significantly mediated the association between treatment and changes in substance use ($\alpha = -0.20$; $\beta = 0.71$). Based on these effect sizes and power estimates for testing mediation derived from a simulation study⁷¹, we will have power greater than 0.80 to detect significant mediating effects with the proposed sample size of 120.

Examining mechanisms of change assumes that treatment influences change in the clinical outcome measures at follow-up, thus we also estimated the power to detect a main effect of treatment on the clinical outcome measures. Effect size estimates were drawn from prior studies of ACT for patients with chronic pain^{5,23,60,72} and MBRP for substance use disorders^{52,63,73}. The effect sizes for ACT in comparison to treatment as usual or active treatment for chronic pain have ranged from 0.29 to 1.09. The effect sizes for MBRP in comparison to treatment as usual for substance use and craving have ranged from 0.21 to 0.52. Based on these studies, we estimate a minimum average effect size of $d=0.25$. Using a mixed-effects linear model with $\alpha=0.05$ (two-tailed test), three repeated assessments (baseline, end of treatment, 6-month follow-up), and a correlation among repeated measures of 0.43 (based on prior studies) we will need 60 subjects per condition (total $n = 120$) for 80% power to detect a main effect of ACT+MBRP in comparison to standard care.

Treatment Assignment Procedures

We will use a random order variable-sized block randomization procedure with block sizes of 2, 4, and 6. The investigators will be blind to the size of each block and randomization allocation.

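### The Aim 2 mediation models leave the mechanism-to-outcome path open to confounding: no covariate rule is aimed at it and no sensitivity analysis is planned

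*Combined protocol and SAP*

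**What the plan says.** Section 9.1 (secondary aim analyses) fits latent growth curves to each mechanism and asks whether its intercept or slope would "mediate the effect of treatment on 6-month clinical outcomes, controlling for baseline levels of the outcomes". On estimation, "models will be estimated using the product of coefficients method": the treatment-to-mechanism coefficient (here a) times the mechanism-to-outcome coefficient (here b). On inference, "We will use bootstrapping to obtain 95% confidence intervals of the mediated effect".

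The baseline outcome is the only covariate named for these models. Two general rules in Section 9.1 can add others:
- Arm imbalance: "Subsequent analyses will adjust for significant baseline differences among the randomized groups".
- Missing data: "Study variables associated with missing data will be covaried in all analyses".

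Section 9.6 addresses confounding in one sentence. It opens with "We do not anticipate any confounding variables" and continues "although we will assess for the role of gender, age, ethnicity, educational achievement, pain duration, and pain location in influencing dependent variables". It does not commit to putting those six variables into the mediation models. The six do not include pain intensity, distress or SCID opioid abuse/dependence.

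The plan does not state an assumption of no unmeasured mechanism-outcome confounding, and it has no sensitivity analysis for b.

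**The concern.** Treatment is randomised, so a has a causal reading. The mechanism slope is not randomised. Within each arm, b is an observational association between a participant's own trajectory and that participant's later outcome. Someone who enters with less distress or milder pain may gain acceptance faster and also do better at six months, even if acceptance itself does nothing.

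The existing covariate rules select on the wrong property. Imbalance between arms does not bear on the association between slope and outcome within arms. Predictors of missingness may or may not be confounders of b.

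At stake is the Aim 2 claim about which mechanisms carry the treatment effect, which is meant to inform a larger trial. The plan states power above 0.80 for these tests, so they will be read as inferential.

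**Working it through.** **The plan's own figure.** Section 9.2 states power above 0.80 for mediation with 120 participants. Joint-significance power, P(a significant) × P(b significant), for the first cited pair (a = 0.56, b = −0.43) is 0.997, 0.858 or 0.990, depending on how the coefficients are scaled. That agrees with the plan. The second pair (a = −0.20, b = 0.71) gives 0.584, 0.191 or 0.602, which does not. That is a separate matter and does not decide this point.

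**Inputs from the plan.** N = 120 allocated 1:1; a = 0.56 or 0.20 in size (9.2); correlation among repeated measures 0.43 (9.2); baseline outcome adjusted (9.1).

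**Assumptions.** Treatment is coded 0/1 and other variables have SD 1. True b = 0. One omitted baseline factor U correlates r with both slope M (within arm) and 6-month outcome Y, and q with baseline outcome Y0. The baseline-to-follow-up correlation of Y is 0.43. An ordinary regression variable stands in for the latent slope, and a Monte Carlo interval for the bootstrap.

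**Spurious b.** Given arm and Y0, Cov(M, Y) = r(r − 0.43q), Var(M) = 1 − r²q² and Var(Y) = 1 − 0.43² = 0.815. Hence

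b = r(r − 0.43q)/(1 − r²q²), and partial correlation = r(r − 0.43q)/√[(1 − r²q²) × 0.815].

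Example with r = 0.5, q = 0.3: b = 0.5 × 0.371/0.9775 = 0.19; partial correlation = 0.1855/√(0.9775 × 0.815) = 0.21.

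**False-mediation rate.** With 120 participants a partial correlation beyond about 0.181 is significant. The chance of that follows from Fisher's z with standard error 1/√115. For a = 0.56 the noncentrality is 0.56 × √(0.25 × 120) = 3.07, so P(a significant) = 0.86. The product of the two probabilities checks the simulation:

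| q | r | spurious b | partial corr. | P(b signif.) | × 0.86 | simulated |
|---|---|---|---|---|---|---|
| 0.3 | 0.3 | 0.05 | 0.06 | 0.09 | 8% | 8% |
| 0.3 | 0.4 | 0.11 | 0.12 | 0.26 | 22% | 23% |
| 0.3 | 0.5 | 0.19 | 0.21 | 0.62 | 53% | 53% |
| 0.5 | 0.3 | 0.03 | 0.03 | 0.06 | 5% | 6% |
| 0.5 | 0.4 | 0.08 | 0.08 | 0.15 | 13% | 13% |
| 0.5 | 0.5 | 0.15 | 0.16 | 0.42 | 36% | 37% |

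Repeat simulation runs differ by up to about two percentage points.

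**Where the problem fades.**
- At r = 0.2 the rate is about 5%, so there is no inflation.
- With a = 0.20, P(a significant) = 0.19. The worst case (r = 0.5) simulates at about 7 to 10%; the product gives 0.19 × 0.42 = 8% and 0.19 × 0.62 = 12%. At smaller r it stays below 5%.
- With a = 0 the worst case is about 0.05 × 0.62 = 3%.

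**With U in the model.** The simulated rate returns to about 4 to 5%.

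**Benchmark for a sensitivity report.** With residual SDs of 1, the residual slope-outcome correlation that would fully explain b is b/√(1 + b²): 0.43/√1.185 = 0.395 and 0.71/√1.504 = 0.579 for the two cited values.

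**The case against.** A reader might infer four stronger things that the documents do not support.

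- That the plan adjusts for nothing beyond the baseline outcome. The imbalance and missingness rules can add covariates, and pain intensity is among the characteristics compared for attrition. The mechanism's initial level is a model term. In the opioid misuse model, baseline misuse is the baseline outcome and so is controlled. Figure 2 is not available and is captioned as simplified. What remains is that none of these terms is chosen because it confounds b.
- That any shared prognostic factor produces false mediation. It also needs a real a-path, as the 0.20 and zero cases show.
- That the error is as large as a simulation without the baseline outcome suggests. That version gives about 13, 35 and 68%, but it is not the planned model.
- That the choice of intermediate endpoints is undermined. Section 9.1 ties Hypothesis 2 to sensitivity to change, judged by the largest slope, and not to b.

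It is also fair to say that the Section 9.6 sentence may have the randomised comparison in mind, where it is reasonable. The mediators are measured before the 6-month outcome, which limits reverse causation. The aim is secondary and speaks of potential mechanisms in a feasibility trial. All of this bears on how serious the gap is. None of it supplies a rule for the mechanism-outcome path.

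**Conclusion.** The point stands in a limited form. The mechanism-to-outcome path is observational, the plan expects no confounding, and nothing in it targets or probes confounding of that path. If treatment moves the mechanism about as much as the first cited effect (0.56), a factor correlated 0.4 to 0.5 with both slope and outcome gives false mediation in about 13 to 53% of trials despite the planned baseline adjustment. At 0.3 the excess is small (about 6 to 8%), and at 0.2 there is none. With a treatment-to-mechanism effect of 0.20 the rate is roughly 10% at worst.

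These rates rest on assumed correlations that the documents neither give nor rule out, and on a simplified model in place of the latent growth curve. This should be corrected before analysis. It does not threaten the primary feasibility aim.

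**What to change.** - **Section 9.6:** delete "We do not anticipate any confounding variables" and refer to the covariate set in 9.1.
- **Section 9.1, covariates:** put one fixed set in both the slope equation and the outcome equation of every mediation model: baseline outcome, baseline pain intensity, a baseline distress measure, SCID opioid abuse/dependence, age and sex. For distress, use the BC-MDI or the diary distress item, whichever is collected at Visit 1. The schedule in 6.1 marks weekly assessments at that visit, but the baseline list in 6.2.2 names neither measure, so this needs settling.
- **Section 9.1, baseline mechanism:** let the latent intercept represent it and include its path to the outcome. Adding the observed baseline score as well would use the same information twice if Visit 1 is the first growth occasion.
- **Section 9.1, reporting:** for each mediated effect, give the residual slope-outcome correlation that would bring it to zero. Describe mediated effects as associations that rest on no unmeasured mechanism-outcome confounding.

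Cost: plan wording and a few model terms, with no new data provided the distress measure is taken at Visit 1. Even eight covariates explaining an assumed 10 to 30% of the mediator would lower power for the first cited pair only from 0.858 to 0.855–0.838 with 120 participants (a loss of 0.02 or less), and from 0.764 to 0.757–0.726 with 96 (20% dropout). The remaining price is more cautious claims.

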10. DATA COLLECTION AND QUALITY ASSURANCE

10.1 Data Collection Forms

All data will be collected by study RAs in a pen-and-paper format. Each participant's data will be coded with their Personal ID number (PID).

10.2 Data Management

All initial data storage will be performed by study RAs. It will be double entered and checked for accuracy. All data will be stored initially at the Albuquerque VA on a password-protected computer in a locked office within a patrolled area (Co-I [name] office). Once all data are collected and ready for analysis, data will be transported to the Department of Psychology onto a password-protected computer in a locked office suite (PI [name] laboratory space) for data analysis. At the time of transport, data will be de-identified and a back-up copy will be kept on the VA premises. All data collection forms are displayed in Appendix IV and detailed in Section 6.2.

Commented [KVS]: Comment 8 – Type of database used to capture study information; whether it will have an audit trail

10.3 Quality Assurance

10.3.1 Training

All staff will complete the human participants protection training required by the University of New Mexico (UNM). The University uses the "CITI" training program (Collaborative Institutional Training Initiative; <https://www.citiprogram.org/>). All study members have completed the "Social and Behavioral Research" Training program, which includes 13 modules, including:

- History and Ethical Principles

- Defining Research with Human Subjects
- The Federal Regulations
- Assessing Risk
- Informed Consent
- Privacy and Confidentiality
- Research with Prisoners
- Research with Children
- Research in Public Elementary and Secondary Schools
- International Research
- Internet-Based Research
- Conflicts of Interest in Research Involving Human Subjects
- Unanticipated Problems and Reporting Requirements in Social and Behavioral Research

All staff must provide at least 80% correct responses to pass a required test on each module. A refresher course must be passed every 24 months.

10.3.2 Quality Control Committee

There is not a quality control committee. Therapist adherence to the study protocol will be assessed as detailed in section 5.4.1.

10.3.3 Metrics

All self-report outcome measures have demonstrated psychometric soundness, including reliability and validity. Please see sections 6.6.2 and 6.6.4 for details and supporting citations.

10.3.4 Protocol Deviations

Protocol deviations will be recorded on the Protocol Deviation Tracking Log and, if appropriate, on the Adverse Events Form and, if necessary the Serious Adverse Events Form (although as noted, we do not foresee any reasonable risk of Serious Adverse Events). See Appendix VIII for all forms.

10.3.5 Monitoring

We will monitor data and safety issues throughout the study. See Data and Safety Monitoring Log in Appendix IX. The study RA will be responsible for completion of the log, which will be reviewed by the Steering Committee at their monthly meeting.

As noted in section 7.6, we have also established a DSMB. The DSMB will meet at least yearly to review Data and Safety Monitoring Logs. In addition, all adverse events will be reported to the DSMB on a monthly basis to allow for ad hoc DSMB meetings should the Board determine they are necessary. Any Serious Adverse Event will be reported to the DSMB within 5 days and will occasion a meeting of the full Board to review the event within 30 days.

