- Current Opioid Misuse Measure (COMM) - We will also collect information on current opioid misuse using the COMM, a measure of aberrant opioid-related behaviors over the past month³. The recommended cut-score of 12 has adequate sensitivity (77%) and specificity (77%) for a current diagnosis of prescription drug abuse³.
- Structured Clinical Interview for DSM-IV (SCID) – The Substance Abuse and Dependence module of the SCID will be conducted with all participants.

Clinical Outcomes:

- Pain Behavior - *PROMIS Bank v1.0 Pain Behavior*
- Pain Interference - *PROMIS Bank v1.0 Pain Interference*
- Disability – *Sickness Impact Profile* (SIP) – The SIP is a measure of health-related disability⁴. It has demonstrated utility in chronic pain settings and provides a detailed assessment of

functioning across multiple domains. The SIP has been widely used in chronic pain settings and has demonstrated sensitivity to intervention^{5,59,60}.

- Pain intensity, including current and least/most/usual over the past week, will be assessed via a 0 (no pain) -10 (maximum possible pain) numerical rating scale (NRS). Assessing pain intensity via NRS is a widely-used and well-established method in studies of pain^{61,62}.

Randomization

Randomization will occur following baseline assessment. We will use a random order variable-sized block randomization procedure with block sizes of 2, 4, and 6. The investigators will be blind to the size of each block and randomization allocation.

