6.2.3 Blinding

PI [name] and Co-I's [name] (study statistician), [name], and [name] will be blinded. Unblinded staff will include the Research Coordinator from the Biomedical Institute of New Mexico (BRINM) and Graduate Research Assistant as these individuals will handle randomization and delivery of treatment, respectively. These individuals will have no access to data and no involvement in data monitoring or analyses.

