12. COMMITTEES

12.1 Steering Committee – Study PI ([name]) and Co-I's (Drs. [name], [name], and [name]) and RAs (TBD) will meet monthly to discuss study progress relative to milestones, coordinate efforts, and review any protocol violations or other issues requiring adjustment.

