Appendix IX

Data and Safety Monitoring Log

Table 1. Enrollment by Month of Study

Month	# Expected	# Screened	# Enrolled or Randomized	# Withdrawn	# Actual (# Enrolled - # Withdrawn)	# Cumulative (Sum of # Actual by Month)

*Enrollment can also be displayed graphically in a Figure, with cumulative subject accrual plotted over time.

Table 2. Demographics

Characteristics	N	N%
Gender		
Female		
Male		
Ethnicity		
Hispanic or Latino		
Not Hispanic or Latino		
Unknown		
Age	Mean (SE)	
Race		
	AIAN	
	Asian	
	Nat Hawaiian/Other Pac	
	Islander	
	Black or African American	
	White	
	Other	
	More than one race	
	Unknown	

Table 3. Subject Status

Pt Identifier	Date Enrolled	Date Completed Study	Study Status	Reason for Withdrawal	% Adherence to Intervention	Intervention Duration (Weeks)

Status: % Compliance to Intervention:

Status.

A = Active
C = Completed

C = Completed

W = Withdraw
L = Lost to followup

% Compliance to Intervention

% Compliance to intervention:
(# tablets taken/total # per protocol)*100

(#)

or
(#)

(# classes taken/total # of sessions should have attended per protocol)*100

Table 4. Adverse Events

Pt Identifier	AE Onset	AE End	AE Code (MedRA, CTCA E)	Severity	SAE ? (Y/N)	Relatedness	Action Taken	Outcome	Comments

Severity of AE:

1 = Mild
 2 = Moderate
 3 = Severe
 4 = Life threatening or disabling

Relatedness to Intervention:

0 = Definitely unrelated
 1 = Unlikely
 2 = Possibly related
 3 = Probably related
 4 = Definitely related

Action Taken:

0 = None
 1 = Dose modification
 2 = Medical intervention (specify in comments)
 3 = Hospitalization
 4 = Intervention discontinued
 5 = Other

Outcome:
 1 = Resolved
 2 = Recovered with minor sequelae
 3 = Recovered with major sequelae
 4 = Continuing treatment
 5 = Condition worsening
 6 = Patient death**

**Provide further details regarding all reported serious AEs and deaths in the SAE and Subject Deaths tables listed at the end of this section.

Table 5. Serious Adverse Events

Pt Identifier	Age	Treatment Date	SAE	SAE Date	Related to Intervention	Description of Actions and Outcomes (e.g., hospitalization, withdrawn from study)

Table 6. Subject Deaths

Pt Identifier	DOB	Date Enrolled	Treatment Date	Cause of Death	Date of Death	Comments

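### The investigators declared blind to allocation review a monthly per-participant log of class attendance, from which most or all allocations can be inferred

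*Combined protocol and SAP*

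**What the plan says.** **Who is blind.** Section 6.2.3: "PI [name] and Co-I's [name] (study statistician), [name], and [name] will be blinded". Section 6.2.2, repeated in Section 9.2: "The investigators will be blind to the size of each block and randomization allocation". Section 6.2.3 names two unblinded roles, the Research Coordinator who handles randomization and the Graduate Research Assistant who delivers treatment. It bars both from data access, data monitoring and analysis.

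**Who reads the log.** Under Section 10.3.5 the study RA fills in the log, "which will be reviewed by the Steering Committee at their monthly meeting". Section 12.1 defines the committee: "Study PI ([name]) and Co-I's (Drs. [name], [name], and [name]) and RAs (TBD) will meet monthly to discuss study progress".

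**What the log shows.** Table 3 (Subject Status) in Appendix IX is laid out by participant identifier. One column is headed % "Adherence to Intervention" and the next gives intervention duration in weeks. The footnote offers two formulas. One counts tablets and is left over from a template. The other divides classes taken by the sessions due under the protocol.

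No section gives blinded members a masked copy, withholds Table 3 from them, or restricts it to the DSMB.

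**The concern.** A column of class attendance works as an arm indicator when only one arm has classes. The people declared blind are, by role and number, the people who read that column every month, so the blinding is undone by the plan's own monitoring procedure, without anyone breaking a rule.

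What is at stake is the discretion left open until data are seen. Section 9.1 has distributions checked and transformed if needed and outliers examined, without giving criteria. Choices of that kind can shift a treatment or mediation estimate in the secondary-aim models. A statistician who does not know the arms cannot steer them, even unintentionally. A later report that the statistician was blinded would also be hard to defend against the log.

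**Working it through.** The plan states no figure on this point, so the check is a side-by-side reading followed by a count.

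**Step 1: do the two groups of people coincide?** Section 6.2.3 blinds one PI and three co-investigators, the statistician among the three. Section 12.1 seats one PI and three co-investigators, plus RAs. Names are removed, so the statistician's seat is inferred from matching counts and roles.

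**Step 2: what can a row contain?** Adherence = (classes taken ÷ sessions due) × 100. An ACT+MBRP participant has 12 weekly sessions in the plan (8 ACT + 4 MBRP). A standard-care participant has none, so the formula gives 0 ÷ 0, which is undefined. The natural entry is blank or not applicable, although the documents do not say so. Section 5.4 plans to track attendance for all participants, which leaves a 0% entry for controls possible.

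**Step 3: how many allocations are disclosed?** Inputs are n = 120 and 60 per arm (Section 9.2). Let *k* be the number of ACT+MBRP participants who never attend. The documents give no rate, so 0%, 10% and 20% of 60 are assumed, that is *k* = 0, 6 and 12.

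*Control rows blank.* An entry means ACT+MBRP and a blank means control. Once groups have started, 120 of 120 are disclosed for any *k*.

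*Control rows entered as 0%.* Any positive value marks ACT+MBRP with certainty. A zero is guessed to be control, and the guess is wrong for the *k* never-attenders.

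| Never attend | Positive rows, 60 − k | Zero rows, 60 + k | Controls among zero rows | Correct overall, (120 − k) ÷ 120 |
|---|---|---|---|---|
| 0% (k = 0) | 60 | 60 | 60/60 = 100% | 120/120 = 100% |
| 10% (k = 6) | 54 | 66 | 60/66 = 91% | 114/120 = 95% |
| 20% (k = 12) | 48 | 72 | 60/72 = 83% | 108/120 = 90% |

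In either case, an ACT+MBRP participant still waiting for a group cannot yet be told from a control. Section 4.3 expects that wait to be under a month for most participants.

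**Step 4: is the separation of unblinded staff consistent?** Section 6.2.3 keeps the treatment-delivering research assistant out of data monitoring. Section 5.2 describes the therapists as RAs, Section 10.3.5 has the study RA complete the log, and Section 12.1 puts RAs on the committee. Nothing separates therapist RAs from those who keep the log or attend the meeting.

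**The case against.** **Blinding was never claimed.** Section 5.2 says condition cannot be blinded. That sentence stands in the section on delivering the interventions, and Section 6.2.3 then declares named roles blinded. If Section 5.2 were meant to govern, Sections 6.2.2, 6.2.3 and 9.2 would be wrong and would still need changing.

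**The log is a template.** The tablets formula shows incomplete adaptation. But the classes formula fits this trial, and Section 10.3.5 adopts the log as an operating document.

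**The disclosure is partly inferred.** This stands. A reader might conclude that all 120 allocations are revealed with certainty. The log has no arm column and the plan does not say how control rows are filled, so that is one case among those tabulated. A reader might also take it as stated that the committee's RAs are the therapists. Section 12.1 leaves the RAs to be determined. RAs also handle consent, baseline assessment and data entry, so overlap is likely but not documented.

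**Little depends on it.** Much of this stands. The primary aim is descriptive (Sections 9.1 and 9.5.1) and the clinical outcomes are self-reported, so investigators' knowledge of arm does not enter scoring. A reader might infer that blinding is the only safeguard on analysis choices. The plan does not support that: baseline covariates follow a 0.05 rule (Section 9.1), and variables associated with missingness are to be included as covariates throughout. Transformations and outliers remain open.

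**Removing two columns would not restore blinding.** This also stands. Reason for withdrawal (Table 3), the code for a discontinued intervention (Table 4) and treatment dates (Tables 5 and 6) can disclose arm. So can the weekly practice and homework items, and the attendance data needed for the retention categories. Outside the log, the VA co-investigator assesses adverse events (Section 7).

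**Conclusion.** The blinding stated in Sections 6.2.2, 6.2.3 and 9.2 is a property the trial does not have as written, because Sections 10.3.5 and 12.1 give the blinded investigators a log from which most or all allocations can be inferred. The 90–100% range under 0% coding depends on the assumed never-attender rate. That this reaches the statistician rests on the inferred committee seat.

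The consequence is limited. It touches transformation and outlier decisions in the secondary-aim growth and mediation models, and the credibility of any later statement that investigators were blind. A reader might infer biased outcome measurement or a compromised feasibility result; the self-reported measures and the descriptive primary aim give no support for either. The point should be corrected, but it does not threaten the trial's main purpose.

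**What to change.** 1. Give blinded committee members a masked log: Table 3 without the adherence and duration columns, and with arm-disclosing entries masked throughout (reason for withdrawal, the discontinued-intervention code, treatment dates). Report adherence to them as one pooled figure, so that monthly feasibility monitoring continues.
2. Send the full log only to the DSMB, which already reviews it under Section 10.3.5, and to unblinded staff.
3. Reconcile Section 6.2.3's bar on unblinded staff in data monitoring with the RA roles in Sections 10.3.5 and 12.1. State which RAs deliver therapy, which complete the log and which attend the committee.
4. Fix transformation and outlier decisions before the statistician sees arm codes, attendance, or the practice and homework items. Masked arm codes alone are not enough, because those variables identify the arm.
5. If this is not workable, withdraw the blinding claim in Sections 6.2.2, 6.2.3 and 9.2.

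The cost is small but not nil: a second copy of the log must be prepared, and blinded members lose sight of individual adherence at monthly meetings in a trial where adherence bears on feasibility. The DSMB need meet only yearly, so the pooled monthly figure is what keeps adherence under regular review.
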